2.2 Secondary objectives

1. Collection of clinical outcome data in this limited patient population
 - a. Progression free survival (PFS), Objective response rate (ORR) and Clinical benefit rate (defined as CR+PR+ stable disease at any tumor assessment) and clinical benefit rate at 6 months (CBR6) (defined as CR+PR+ stable disease for at least 6 months) in the entire cohort, and the ESR1-mt cohorts
2. Correlation between longitudinal changes in circulating levels of ESR1 mutations and clinical outcome
3. Assessment of concordance of ESR1 status in plasma and biopsy samples
4. Use of cfRNA to determine gene expression in AI resistant mutant ESR1 MBC

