4. SUBJECT SELECTION CRITERIA

4.1 Inclusion criteria

For inclusion in the study subjects should fulfill the following criteria:

1. Signed informed consent
2. Patients must have histologically or cytologically confirmed invasive breast cancer that is ER+ (>1% staining) with radiographical or clinical evidence of metastatic disease
 - a. Measurable and/or non-measurable disease
3. Prior therapies:
 - a. Patients must have previously received an aromatase inhibitor in the adjuvant, neo-adjuvant or metastatic setting.

- b. Patients must have previously received palbociclib in the adjuvant, neo-adjuvant or metastatic setting. If patient is currently taking palbociclib at time of screening for the trial they may continue taking palbociclib.
 - c. The minimum duration of AI in the adjuvant setting is 2 years.
 - d. There is no minimum duration of AI in the metastatic setting or neoadjuvant setting.
 - e. Patients may have been previously treated with an mTOR inhibitor or other investigational agent in addition to an aromatase inhibitor.
 - f. Prior treatment with tamoxifen is allowed in the adjuvant setting provided that it was followed by a minimum of 2 years of an AI.
4. Brain metastasis is allowed if previously treated, stable and off steroids for a minimum of 56 days
5. Age > 18 years
6. Male or female breast cancer is allowed
7. Patients may be pre- or post-menopausal; pre-menopausal patients must be on ovarian suppression and must be adequately suppressed on LHRH agonists with estradiol levels in the post-menopausal range
 - a. Premenopausal patients cannot be pregnant and must agree to adequate birth control in addition to ovarian suppression. Agreement by the patient and/or partner to use highly effective, nonhormonal form of contraception or two effective forms of non-hormonal contraception. Contraception use should continue during the duration of study treatment and for at least 6 months after the last dose of study treatment.
8. ECOG performance status 0-2
9. Adequate bone marrow function as indicated by the following, within 14 days of enrollment:
 - a. ANC \geq 1500 cells/mm³
 - b. Platelets \geq 100,000 cells/ mm³
 - c. Hemoglobin \geq 9 g/dL
10. Adequate liver function, as indicated by the following, within 14 days of enrollment.
 - a. Total bilirubin \leq 1.5 \times upper limit of normal (ULN)
 - b. AST \leq 1.5 \times ULN
 - c. ALT \leq 2.5 \times ULN

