5.6 Procedures for discontinuation of a subject from treatment

All patients who initiate protocol treatment will be included in the overall evaluation of response as part of the ITT analysis. All reasons for discontinuation of treatment should be documented clearly in the study record. In case of treatment discontinuation due to unacceptable toxicity as defined in section 6.4, the patients will still be included in the overall evaluation of response by ITT. If the study medication is discontinued at the patient's own request, the reason for discontinuation from the study must be documented and the patient followed for outcomes by ITT analysis.

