6.3.4 Response Assessment

Target Lesions

When more than one measurable lesion is present at baseline all lesions up to a maximum of five lesions total (and a maximum of two lesions per organ) representative of all involved organs should be identified as **target lesions** and will be recorded and measured at baseline (this means in instances where patients have only one or two organ sites involved a maximum of two and four lesions respectively will be recorded).

Evaluation of Target Lesions

- Complete Response (CR): Disappearance of all target lesions. Any pathological lymph nodes (whether target or non-target) must have reduction in short axis to <10 mm.
- Partial Response (PR): At least a 30% decrease in the sum of diameters of target lesions, taking as reference the baseline sum diameters.
- Progressive Disease (PD): At least a 20% increase in the sum of diameters of target lesions, taking as reference the smallest sum on study (this includes the baseline sum if that is the smallest on study). In addition to the relative increase of 20%, the sum must also demonstrate an absolute increase of at least 5 mm. (Note: the appearance of one or more new lesions is also considered progression).
- Stable Disease (SD): Neither sufficient shrinkage to qualify for PR nor sufficient

increase to qualify for PD, taking as reference the smallest sum of diameters while on study.

Non-target lesions

All other lesions (or sites of disease) including pathological lymph nodes should be identified as **non-target lesions** and should also be recorded at baseline. Measurements are not required and these lesions should be followed as ‘present’, ‘absent’, or in rare cases ‘unequivocal progression’. In exceptional circumstances, unequivocal progression in non-target lesions may be accepted as disease progression. In addition, it is possible to record multiple non-target lesions involving the same organ as a single item on the case record form (e.g. ‘multiple enlarged pelvic lymph nodes’ or ‘multiple liver metastases’).

When the patient only has non-measurable disease, the increase in overall disease burden should be comparable in magnitude to the increase that would be required to declare PD for measurable disease: i.e., an increase in tumor burden from “trace” to “large”, an increase in nodal disease from “localized” to “widespread”, or an increase sufficient to require a change in therapy.

Evaluation of Non-Target Lesions

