- Complete Response (CR): Disappearance of all non-target lesions and normalisation of tumor marker level. All lymph nodes must be non-pathological in size (<10mm short axis).
- Non-CR/Non-PD: Persistence of one or more non-target lesion(s) and/or maintenance of tumor marker level above the normal limits.
- Progressive Disease (PD): Unequivocal progression of existing non-target lesions. (Note: the appearance of one or more new lesions is also considered progression).

Evaluation of Best Overall Response

The best overall response is the best response recorded from the start of the treatment until disease progression/recurrence (taking as reference for progressive disease the smallest measurements recorded since the treatment started). The patient’s best overall response assignment will depend on the findings of both target and non-target disease and will also take into consideration the appearance of new lesions.

TABLE 2. Time to response definition

Target Lesions	Non-Target Lesions	New Lesions	Overall Response
-----------------------	---------------------------	--------------------	-------------------------

CR	CR	No	CR
CR	Non CR/Non PD	No	PR
CR	Not evaluated	No	PR
PR	Non PD or not all evaluated	No	PR
SD	Non PD or not all evaluated	No	SD
Not all evaluated	Non PD	No	NE
PD	Any	Yes or no	PD
Any	PD	Yes or no	PD
Any	Any	Yes	PD

CR= complete response, PR= partial response, PD= progressive disease, SD= stable disease, NE= not evaluable.

Note: Patients with a global deterioration of health status requiring discontinuation of treatment without objective evidence of disease progression at that time should be reported as “*symptomatic deterioration*”. Every effort should be made to document the objective progression even after discontinuation of treatment.

Progression Free Survival

PFS is defined as the duration of time from time of randomization to time of progression or death, whichever occurs first. PFS for a subject without an event will be censored on the date of last tumor assessment. If an interval of 6 months passes without a tumor assessment, PFS will be censored at the time of the earlier tumor assessment, even if an event (progressive disease or death) is later observed.

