11. EVALUATION AND CALCULATION OF VARIABLES

11.1 Calculation or derivation of efficacy variable(s)

The primary objectives of the study are descriptive assessments of ESR1 mutation detection in plasma. One of the secondary endpoints of the study is PFS. PFS is defined as the duration of time from time of randomization to time of progression or death, whichever occurs first. PFS for a subject without an event will be censored on the date of last tumor assessment. If an interval of 6 months passes without a tumor assessment, PFS will be censored at the time of the earlier tumor assessment, even if an event (progressive disease or death) is later observed. If a patient has not had an event, PFS will be censored at the date of the last adequate tumor evaluation. PFS will also be censored at the date of tumor evaluation when the next tumor evaluation (or death) is >6 months after the previous evaluation without an event. PFS will be assessed via local radiology assessment according to RECIST 1.1.

Although central review may occur as part of site calibration or an audit, the local assessment will be considered as the basis for the primary efficacy analysis. In the absence of measurable disease at baseline, the following criteria (per RECIST 1.1) will be used to assess disease progression among the patients with nonmeasurable lytic or mixed (lytic + blastic) bone lesions: 1) The appearance of one or more new lesions or 2) Unequivocal progression of existing non-measurable lesions.

Additional secondary endpoints include response rate, clinical benefit rate, (defined as CR+PR+ SD at any tumor assessment), clinical benefit rate at 6 months (CBR6), in the entire cohort, and the ESR1-mut cohorts. Response rate will be reported from best overall response according to RECIST 1.1 and as described in section 6.3. The response rate will then be compared amongst the tamoxifen plus palbociclib and fulvestrant plus palbociclib arms in the entire cohort and in the subgroup of ESR1-mt patients.

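### Response rate is computed over the whole cohort, including patients with only non-measurable disease who can respond only by CR, so ORR is diluted and hard to interpret (minor).

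*Combined protocol and SAP*

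**What the plan says.** - **Eligibility (4.1, item 2a):** "Measurable and/or non-measurable disease". A patient with no measurable lesion can enrol.
- **Partial response (6.3.4):** "At least a 30% decrease in the sum of diameters of target lesions". Target lesions are chosen from measurable lesions.
- **Non-target disease (6.3.4):** there are three outcomes. CR is "Disappearance of all non-target lesions and normalisation of tumor marker level". The middle category is "Persistence of one or more non-target lesion(s) and/or maintenance of tumor marker level above the normal limits". The third is PD. None of them is a PR, and every PR row of Table 2 has target lesions in CR or PR.
- **Response rate (11.1):** "Response rate will be reported from best overall response according to RECIST 1.1", then compared between arms "in the entire cohort and in the subgroup of ESR1-mt patients". Section 2.2 sets the same population for ORR: "in the entire cohort, and the ESR1-mt cohorts".
- **Analysis set (5.6):** "All patients who initiate protocol treatment will be included in the overall evaluation of response as part of the ITT analysis".
- **Test (12.1):** mid-P Fisher for the univariate comparison, with logistic regression for exploratory multivariable models. Measurability is not named as a covariate.

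The special rule in 11.1 for patients without measurable disease deals with progression, not response. Section 3.1 gives 1:1 randomisation, and no stratification factor is stated.

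**The concern.** The denominator of the response rate includes patients who have only one route into the numerator. Anyone without a target lesion needs complete disappearance of disease to be counted. A patient with measurable disease needs only a 30% shrinkage.

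This group may not be small. Section 6.3.2 classes blastic bone lesions as non-measurable, and section 6.3.5 itself anticipates bone-only disease.

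Whole-cohort ORR therefore mixes drug activity with the proportion of enrolled patients who happen to have measurable lesions. Section 12.2 says the results are meant to help prioritise and inform later studies. An ORR that moves with the share of non-measurable disease transfers poorly to a trial with a different mix.

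**Working it through.** The documents contain no ORR assumption, power figure or alpha for response, so there is no planned figure to reproduce. What follows is illustrative.

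**Inputs from the documents:** 40 patients, 20 per arm (12.2); 1:1 allocation with no stated stratification (3.1); mid-P Fisher, two-sided (12.1); about 25% expected to carry an ESR1 mutation (6.3.5).

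**Assumed inputs:** p, f and c as listed in each step; alpha 0.05.

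**1. Dilution.** Whole-cohort ORR = p(1 - f) + c·f.

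With p = 25% and c = 0:
- f = 25%: 0.25 × 0.75 = 18.75%, about 19%
- f = 40%: 0.25 × 0.60 = 15%
- f = 50%: 0.25 × 0.50 = 12.5%

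With c = 5%, f = 40% gives 0.15 + 0.05 × 0.40 = 17%. The c = 0 figures are the worst case.

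**2. Chance imbalance.** If 16 of 40 patients have only non-measurable disease, the number X falling in one arm is hypergeometric (40, 16, 20). The arms differ by 4 or more such patients when X ≤ 6 or X ≥ 10, with probability 0.333. For 8, 12 or 20 such patients the probability is 24%, 30% or 34%.

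A 6 vs 10 split with identical drugs, p = 25% and c = 0 gives expected rates of 14 × 0.25/20 = 17.5% and 10 × 0.25/20 = 12.5%. That is 3.5 against 2.5 responders, a difference of one patient.

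**3. False-positive rate.** Exact enumeration of the mid-P Fisher test, p = 25% in both arms, c = 0, 16 of 40 non-measurable-only:

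| Analysis | False-positive rate |
|---|---|
| Whole cohort, averaged over random splits | 3.6% |
| Whole cohort, given a 6 vs 10 split | 4.2% |
| Measurable disease only, 12 vs 12 | 4.3% |

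All are below 5%.

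**4. Power.** Rates in measurable disease as shown, f = 40%, c = 0:

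| Scenario | Whole cohort, 20 vs 20 | Measurable only |
|---|---|---|
| 10% vs 40%, exactly 12 measurable per arm | 0.30 | 0.38 |
| 10% vs 40%, averaged over random splits | 0.31 | 0.36 |
| 10% vs 50%, exactly 12 measurable per arm | 0.51 | 0.59 |

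The smaller denominator does not cost power here, because the patients removed are ones who contribute no responses.

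**5. ESR1-mt subgroup.** 25% of 40 is 10 patients, or 5 per arm if evenly split. At f = 40% about 3 per arm would have measurable disease.

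**The case against.** The strongest reply is that whole-cohort ORR is a legitimate and consistently specified quantity: response among all treated patients. Sections 2.2, 5.6 and 11.1 agree on it. It is too low only relative to a measurable-disease ORR, and nothing in the documents makes the present choice a contradiction. That stands. The point concerns which quantity is more useful, not an error of specification.

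A reader might also infer that an uneven share of non-measurable disease will pass as a treatment effect in the Fisher test. The documents do not support this. Randomisation balances the share in expectation, and what remains is ordinary sampling variation, which the test covers over repeated randomisations (step 3). A given trial with a severe split can be affected: with a 5 vs 11 split and p = 30%, the conditional false-positive rate is 8.2%. Gaps of 6 or more arise in about 11% of trials when 16 of 40 are non-measurable-only. That is a reason to tabulate measurability by arm, not evidence of bias.

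A second tempting reading is that these patients are automatic non-responders. Section 6.3.4 allows CR on non-target disease, so they are not.

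Finally, the logistic models in 12.1 could adjust for measurability. They are exploratory and do not name it, so this helps only in part.

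**Conclusion.** The point holds as a minor one. Patients with only non-measurable disease are eligible, cannot have a PR, and stay in the ORR denominator in both the whole cohort and the ESR1-mt subgroup. No section restricts ORR to measurable disease.

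The absolute rate is diluted by an amount the documents do not allow one to fix. Under the assumptions in step 1, a 25% rate would be reported as 12.5% to 19%, and higher if some of these patients reach CR. The comparison between arms gains noise and loses a modest amount of power, roughly 0.05 to 0.08 in the assumed 10% vs 40% case. It does not gain systematic bias or a raised overall false-positive rate.

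Severity is minor. Section 11.1 describes the primary objectives as descriptive, ORR is secondary in a 40-patient pilot, and the thresholds for a promising result in 12.1 are PFS hazard ratios. No decision rule uses ORR.

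**What to change.** In 11.1 and 12.1:

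- Make the ORR comparison in all randomised patients with measurable disease at baseline.
- Keep whole-cohort ORR as a supportive summary, so the present definition is not lost.
- Tabulate baseline measurability by arm, overall and in the ESR1-mt subgroup.

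Align the ORR wording in 2.2 and 5.6 with this. The subset is fixed before treatment, so the randomised comparison is preserved. Target and non-target lesions are already recorded at baseline under 6.3.4, so no new data are needed.

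The cost is a few lines of text and a smaller denominator. In the ESR1-mt subgroup, perhaps 3 per arm under the assumptions above, ORR should be reported descriptively on either definition.

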11.2 Calculation or derivation of safety variable(s)

All adverse events will be captured on the appropriate study-specific case report forms (CRFs) and will be calculated as a frequency of occurrence according to the CTCAE v4.03. The frequency of adverse events will be categorized in accordance to the grading system present in CTCAE v4.03, using the highest grade recorded for each AE for each patient. AE rates will be calculated from the tamoxifen plus palbociclib and fulvestrant plus palbociclib cohorts and compared using the mid-p correction to Fisher's exact test.

12 . STATISTICAL METHODS AND SAMPLE SIZE DETERMINATION

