1.2 Research hypothesis

1. In the 2nd to 3rd line of AI resistant WT ESR1 MBC, Fulvestrant plus palbociclib treatment will result in earlier detection of ESR1 mutations compared to treatment with tamoxifen plus palbociclib
2. In the 2nd to 3rd line of AI resistant mutant ESR1 MBC, Fulvestrant plus palbociclib will result in increased PFS compared with tamoxifen plus palbociclib
3. Change of allele frequency of ESR1 mutation is associated with PFS in all groups

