3. STUDY PLAN AND PROCEDURES

3.1 Overall study design and flow chart

Patients with ER+ breast cancer who had 1 to 3 prior lines of endocrine therapy and up to one line of chemotherapy for MBC, excluding fulvestrant and tamoxifen, will be randomized in a 1:1 ratio to receive fulvestrant 500mg IM Q28 days with one extra dose on D15 of the first cycle (as a loading dose) plus palbociclib 125mg/day PO on a 21 days on/7 days off schedule or tamoxifen 20mg PO daily plus palbociclib 125mg/day PO on a 21 days on/7 days off schedule. Patient accrual will be a goal of 40 evaluable at up to 4 sites. At randomization, plasma will

be obtained for evaluation of ESR1-mt and a biopsy will be obtained when possible. During treatment, all patients will undergo ct-DNA ESR1 mutation evaluation every 28 days. Treatment will continue until disease progression or unacceptable toxicity. At the time of disease progression, a second biopsy will be obtained when possible and the last blood drawn for evaluation of ct-DNA ESR1-mt will occur. All tissue obtained will also undergo molecular analysis to determine the activity of mutant ESR1.

[figure not shown]

FIGURE 5. Study Schema

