6.4 Safety

6.4.1 Definition of adverse events

An adverse event is the development of an undesirable medical condition or the deterioration of a pre-existing medical condition following or during exposure to a pharmaceutical product, whether or not considered causally related to the product. An undesirable medical condition can be symptoms (e.g., nausea, chest pain), signs (e.g., tachycardia, enlarged liver) or the abnormal results of an investigation (e.g., laboratory findings, electrocardiogram). In clinical studies, an AE can include an undesirable medical condition occurring at any time, including run-in or washout periods, even if no study treatment has been administered. The term AE is used to include both serious and non-serious AEs. Definition of AE will be in accordance to

the CTCAE version 4.03. All grades of AE's will be captured, greater than grade 1. AE's will start to be captured on day 1 of study drug administration.

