- L) Fulvestrant will be dosed as follows: 2x250 mg injections on days 1, 15, 29, then next in 4 weeks (day 57) and continuing every 4 weeks thereafter. Tamoxifen will be dosed as follows: Tamoxifen 20mg PO Daily.
- m) All subjects must have a final toxicity assessment at least 30 days following the last dose of study drug
- n) Subjects will be followed approximately every 3 months after completion of study treatment for disease status and survival until death through clinic visit, phone call or record review.

- o) Optional tumor biopsy will be performed \leq 30 days prior to first day of treatment and within 30 days of treatment discontinuation.
- p) Palbociclib will be dosed 125mg PO QD days 1-21 of 28 day cycle
- q) PT, INR, PTT only needs to be repeated for optional biopsies if the patient on anticoagulants

(X) = OPTIONAL

Note: Additional tests may be performed at the discretion of the treating investigator as clinically indicated. The sample collection schedules outlined above are based on an ideal subject. The sample schedule should be followed as closely as is realistically possible; however, the schedule may be modified due to problems such as scheduling delays or conflicts (e.g., clinic closure, poor weather conditions, vacations, etc.).

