12.1 Statistical analysis plan

The primary analysis will be conducted at least 6 months after the last patient is enrolled. Cox proportional hazards regression will be used to estimate hazard ratios comparing PFS for tamoxifen plus palbociclib and fulvestrant plus palbociclib. Fulvestrant will be considered promising for the unselected population if the fitted hazard ratio is < 0.8 , and for the ESR1-mut subpopulation if the hazard ratio is < 0.65 .

Response rate will be compared between treatment arms using the mid-P correction to Fisher's exact test for univariate comparisons, and logistic regression for exploratory multivariable models. Cox proportional hazards regression will be used for analyses with overall survival as the endpoint.

Adverse events will be reported for all patients in the safety cohort defined above, summarized by treatment group. Adverse events and serious adverse events will be tabulated in order of prevalence, with the highest grade reported by each patient.

Concordance of ESR1 status in plasma and biopsy samples will be assessed primarily by agreement regarding presence/absence of mutations for tissue and blood samples collected no more than 30 days apart and without intervening therapy. Kappa statistics adjusted for clustering (both pre-therapy and post-therapy time points for some subjects) will describe basic agreement. Additionally, between-subject and within-subject variation in mutant allele frequency will be compared using linear mixed models and the concordance correlation coefficient. This approach (complementary **analysis of categorical and continuous versions of**

ESR1 mutation status) may also be applied to assessment of within-patient longitudinal change. The primary analysis for these correlative studies will examine presence and allele frequency of any ESR1 mutation. Secondary analyses will examine and compare tissue-blood concordance and longitudinal change in liquid biopsy measures for specific ESR1 mutations. Level and change in circulating levels of ESR1-mt will be assessed as predictors of PFS using Cox proportional hazards regression with time-varying covariates. All hypothesis tests will be two-sided.

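### Section 11.2 tests whole-period crude AE proportions although the AE observation window lasts as long as treatment, so a difference in PFS may appear as a small difference in toxicity

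*Combined protocol and SAP*

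**What the plan says.** Safety and toxicity is the fourth primary objective in section 2.1. Section 11.2 gives the only planned between-arm safety comparison: "AE rates will be calculated from the tamoxifen plus palbociclib and fulvestrant plus palbociclib cohorts and compared using the mid-p correction" to Fisher's exact test. The counting unit is the patient, "using the highest grade recorded for each AE for each patient". A Fisher-type test needs counts of patients with and without the event, so what the text calls rates are crude proportions with no person-time. Section 12.1 adds a by-arm tabulation: "Adverse events and serious adverse events will be tabulated in order of prevalence, with the highest grade reported by each patient".

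The observation window has no common length. Section 3.1: "Treatment will continue until disease progression or unacceptable toxicity". Capture starts with treatment (section 6.4.1: "AE's will start to be captured on day 1 of study drug administration") and ends some time after it (Table 4, footnote m: "All subjects must have a final toxicity assessment at least 30 days following the last dose of study drug").

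The protocol hopes for a PFS difference. For ESR1-mutant disease, section 1.2 (Research hypothesis) states that "Fulvestrant plus palbociclib will result in increased PFS compared with tamoxifen plus palbociclib". Section 3.2 suggests that fulvestrant could prolong PFS relative to tamoxifen more generally. Section 12.1 calls fulvestrant promising if the fitted hazard ratio is below 0.8 in the unselected population, or below 0.65 in the ESR1-mutant subpopulation.

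No section provides for exposure-adjusted incidence, time to first AE, a common fixed window, or a summary of treatment duration by arm.

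**The concern.** A proportion of patients who ever had an AE depends on the AE risk per month and on how many months each patient was watched. Here the second quantity tracks PFS. If PFS is longer on one arm, that arm accumulates more AEs of the kind that arise throughout treatment, and the section 11.2 test cannot tell a more toxic regimen from one taken for longer.

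What is at stake is the reported safety comparison on a listed primary objective. The trial is a pilot whose results are meant to inform later studies (section 12.2), so its AE frequencies are likely to be reused.

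**Working it through.** The plan gives no expected AE frequency, control median or alpha for this comparison, so there is no figure to reproduce. The check asks how large a difference arises when the AE risk per month is identical in both arms.

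**Inputs from the documents.** Whole-arm hazard ratio 0.8 (section 12.1, used as a scenario); about 30 days of AE capture after last dose (Table 4, footnote m), taken as 1 month; analysis at least 6 months after last enrolment (section 12.1); 20 patients per arm (section 12.2).

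**Assumptions.** Exponential PFS with tamoxifen-arm median 5 months; treatment stops only at progression; constant AE hazard *a* of 0.03, 0.10 or 0.30 per month, equal in both arms; two-sided alpha 0.05.

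**Progression hazards.** Tamoxifen m = ln 2 / 5 = 0.1386 per month; fulvestrant 0.8 × 0.1386 = 0.1109. Mean time to progression is 1/0.8 = 1.25 times as long on fulvestrant.

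**Formulas.**
- Counted to progression, no cut-off: P(AE) = a/(a+m).
- Counted to progression plus 1 month, every patient cut at C months: P(AE) = 1 − e^(−a) × (m + aE)/(m+a), with E = e^(−(m+a)(C−1)).
- Counted to progression within the first 56 days (W = 56/30.44 = 1.84 months): P(AE) = a/(a+m) × (1 − e^(−(a+m)W)).

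Example, a = 0.10, no cut-off: 0.10/0.2386 = 41.9% against 0.10/0.2109 = 47.4%. With C = 6: tamoxifen E = e^(−1.193) = 0.303, P = 1 − 0.905 × 0.708 = 35.9%; fulvestrant E = e^(−1.055) = 0.348, P = 1 − 0.905 × 0.691 = 37.5%.

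**Results** (tamoxifen % / fulvestrant %, with the difference in points from unrounded values):

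| Counting | a = 0.03 | a = 0.10 | a = 0.30 |
|---|---|---|---|
| No cut-off, no tail | 17.8 / 21.3 (+3.5) | 41.9 / 47.4 (+5.5) | 68.4 / 73.0 (+4.6) |
| 1-month tail, 12-month cut | 17.5 / 19.2 (+1.7) | 44.7 / 48.2 (+3.5) | 76.2 / 79.4 (+3.2) |
| 1-month tail, 6-month cut | 12.8 / 13.4 (+0.6) | 35.9 / 37.5 (+1.5) | 70.9 / 73.1 (+2.1) |
| First 56 days only | 4.7 / 4.9 (+0.12) | 14.9 / 15.2 (+0.36) | 37.9 / 38.7 (+0.85) |

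In the first row the largest possible gap over any hazard is (1 − √0.8)/(1 + √0.8) = 5.6 points, so the range is not sensitive to the hazards chosen. With tamoxifen medians of 4, 6 and 11 months, a 1-month tail and tamoxifen-arm frequencies of 10% to 90%, the gap is +1.7 to +5.3 points without a cut-off and +0.3 to +2.8 with a 6-month cut for everyone.

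**Against sampling error.** One patient is 1/20 = 5 points. Near 50% the standard error of the difference is √(2 × 0.25/20) = 15.8 points. With a 6-month median, 1-month tail and no cut-off (50% against 55.1%), exact enumeration of the mid-P test gives rejection of 4.9%, against 3.9% under equal exposure. Fulvestrant shows the higher observed frequency in 56.5% of trials, against 43.7% under equal exposure (the rest are ties or the reverse).

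**Early-onset AEs, and the patient-month alternative.** Suppose an AE can occur only in month 1, with hazard 0.7 in both arms and counting to progression. Crude frequency is 47.4% on tamoxifen and 48.0% on fulvestrant, so 11.2 is nearly unbiased. Mean months at risk to first event or progression are (1 − e^(−(a+m)))/(a+m) + e^(−(a+m))/m = 3.80 and 4.69. First events per patient-month are 0.474/3.80 = 0.125 and 0.480/4.69 = 0.102, a ratio of 0.82. The patient-month rate then makes the longer-treated arm look safer when it is not.

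**The case against.** The strongest reply is that this is small, conditional and without consequence. Most of that stands.

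- **Direction.** A reader might infer that exposure differs by design and that the better arm will look more toxic. The documents support neither. A longer PFS on fulvestrant is a hypothesis, and the hazard ratios are cut-offs for a fitted estimate, not expected effects. Section 3.2 itself reports an earlier trial of fulvestrant 250 mg with time to progression of 6.8 months against 8.3 on tamoxifen. If tamoxifen runs longer, the bias reverses.
- **Size.** A reader might apply the 0.65 threshold, which under the no-cut-off model gives gaps of 7 to 11 points. That threshold belongs to the ESR1-mutant subpopulation, whereas 11.2 compares whole arms. With mutations in the 25% that section 6.3.5 expects, and no effect in the rest, the same model gives a whole-arm gap of 1.8 to 2.7 points.
- **Consequence.** A reader might say the plan penalises efficacy. No stopping rule, threshold or go/no-go decision uses the AE test, and section 11.1 describes the primary objectives as descriptive ESR1 assessments. A shift towards higher worst grades is plausible by the same mechanism but has not been quantified.
- **Model.** A constant hazard with no cut-off is the case most favourable to the concern. Section 5.5 also allows stopping for toxicity, patient request or physician discretion. However, the 6-month cut is the opposite extreme: 6 months is the minimum follow-up after the last enrolment, and earlier patients can be observed for longer.
- **Validity.** Crude incidence properly describes what patients experienced.

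What remains is that the crude proportion is the only between-arm comparison, it is tested, and nothing in the plan lets a reader see or remove the part due to treatment duration.

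**Conclusion.** The concern holds in a limited form. If PFS differs between arms, the section 11.2 comparison may show higher frequencies of time-accruing AEs in the longer-treated arm at equal monthly risk. At a whole-arm hazard ratio of 0.8 the spurious difference is about 0.6 to 5.5 points, depending mainly on the data cut-off. This rests on an assumed 5-month tamoxifen median, exponential PFS and constant, equal AE hazards of 0.03 to 0.30 per month. It affects the described frequencies more than the test result, is small beside sampling error at 20 per arm, and hardly touches early-onset AEs. It is worth correcting because the correction is cheap, not because it threatens the trial's conclusions.

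**What to change.** In section 11.2:

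1. Report treatment duration by arm.
2. Make the between-arm comparison on worst grade within a common early window, for example the first two cycles up to the first 8-week assessment. In the model above this cuts the spurious gap to under 1 point.
3. Supplement it with time to first AE, censored 30 days after last dose.
4. Keep the whole-period crude table as descriptive, without a test.
5. If patient-month rates are shown, state that they assume a constant hazard and can make the longer-treated arm look falsely safer for early-onset AEs. They should not be the lead comparison.

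The cost is analysis-plan wording. AE start and stop dates (section 6.4.3), drug diaries in both arms (section 6.2), and the 4-weekly toxicity and 8-weekly imaging schedule (Table 4) are already in place, and no clinical procedure changes. The downside is that the common window misses late events, which the descriptive table and the time-to-first-AE analysis still show.
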